#### Analysis window for Vitals

Visit Week	Target Day	Window Definition
Baseline	1	Last Evaluation prior to or on Study Day 1
Week 2	15	Study Day 2 to 21
Week 4	29	Study Day 22 to 35
Week 6	43	Study Day 36 to 49
Week 8	57	Study Day 50 to 63
Week 10	71	Study Day 64 to 77
Week 12	85	Study Day 78 to 91
Week 14	99	Study Day 92 to 105
Week 16	113	Study Day 106 to 119
Week 18	127	Study Day 120 to 133
Week 20	141	Study Day 134 to 147
Week 22	155	Study Day 148 to 161
Week 24	169	Study Day 162 to 175
Week 26	183	Study Day 176 to 189
Week 28	197	Study Day 190 to 203
Week 30	211	Study Day 204 to 217
Week 32	225	Study Day 218 to 231
Week 34	239	Study Day 232 to 245
Week 36	253	Study Day 246 to 259
Week 38	267	Study Day 260 to 273
Week 40	281	Study Day 274 to 287
Week 42	295	Study Day 288 to 301
Week 44	309	Study Day 302 to 315

Week 46	323	Study Day 316 to 329
Week 48	337	Study Day 330 to 343
Week 50	351	Study Day 344 to 357
Week 52	365	Study Day 358 to 385
Week 58	407	Study Day 386 to 448
Week 70	491	Study Day 449 to 494

Analysis window for EASI and IGA

Visit Week	Target Day	Window Definition
Baseline	1	Last Evaluation after Randomization and prior to or on Study Day 1
Week 4	29	Study Day 2 to 35
Week 6	43	Study Day 36 to 49
Week 8	57	Study Day 50 to 63
Week 10	71	Study Day 64 to 77
Week 12	85	Study Day 78 to 98
Week 16	113	Study Day 99 to 140
Week 24	169	Study Day 141 to 210
Week 36	253	Study Day 211 to 294
Week 48	337	Study Day 295 to 343
Week 50	351	Study Day 344 to 357
Week 52	365	Study Day 358 to 427
Week 70	491	Study Day 428 to 494

Analysis Window for SCORAD, EQ-5D-3L, POEM, DLQI and PGI-S

Visit Week	Target Day	Window Definition
Baseline	1	Last Evaluation prior to or on Study Day 1
Week 4	29	Study Day 2 to 42
Week 8	57	Study Day 43 to 70
Week 12	85	Study Day 71 to 98
Week 16	113	Study Day 99 to 140
Week 24	169	Study Day 141 to 210
Week 36	253	Study Day 211 to 294
Week 48	337	Study Day 295 to 343
Week 50	351	Study Day 344 to 357
Week 52	365	Study Day 358 to 368

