^m Administration of study drug is the final activity performed at a visit. Subjects randomized to Q4W dosing will receive placebo at the visits between dosing with tezepelumab. Subjects will be observed for 2 hours post-treatment at the day 1 and week 2 visits. For all other visits where investigational product is administered, subjects will be observed for a period of time at the discretion of the Investigator.

ⁿ All subjects will receive a 420 mg SC dose of either study drug or placebo as their first dose.

^o Only certain inclusion criteria specified in the protocol will be re-evaluated at the day 1 visit. These criteria will be evaluated prior to any other day 1 study activities and are required to be met for dosing with investigational product.

^p All subjects who terminate the study early will complete an early termination visit consisting of all assessments included in the EOT (week 52) visit. In addition, a safety follow-up visit will occur 18 weeks after the EOT visit.

Table 2-2. Schedule of Activities for Part A and Part B (Week 26 Through End of Study)

	Treatment Period (52 weeks) ^a														EOT ^a /ET ^l	EOS ^a		Unscheduled
	Wk 26	Wk 28	Wk 30	Wk 32	Wk 34	Wk 36	Wk 38	Wk 40	Wk 42	Wk 44	Wk 46	Wk 48	Wk 50	Wk 52	Wk 58	Wk 70		
GENERAL AND SAFETY ASSESSMENTS																		
Physical examination															X	X	X	X
12-lead ECG ^b																	X	X
Vital signs ^c	X	X	X	X	X	X	X	X	X	X	X	X	X	X	X	X	X	X
Adverse events	X	X	X	X	X	X	X	X	X	X	X	X	X	X	X	X	X	X
Serious adverse events	X	X	X	X	X	X	X	X	X	X	X	X	X	X	X	X	X	X
Disease-related events	X	X	X	X	X	X	X	X	X	X	X	X	X	X	X	X	X	X
Concomitant therapies review	X	X	X	X	X	X	X	X	X	X	X	X	X	X	X	X	X	X
LABORATORY ASSESSMENTS																		
Urine pregnancy test ^d		X		X		X		X		X		X		X		X		X
Coagulation													X	X				X
Hematology						X						X		X	X	X		X
Chemistry						X						X		X	X	X		X
Urinalysis (dipstick) ^e						X						X		X	X	X		
Anti-tezepelumab-antibody						X						X					X	X
Serum immunoglobulins ^f					X							X		X				X
PPD or Quantiferon GOLD														X				
STUDY-SPECIFIC ASSESSMENTS																		
Electronic diary ^g	Completed in the morning at home on eDiary																X	X
Assessment of EASI and IGA						X							X	X	X		X	
SCORAD						X							X	X	X			
EQ-5D-3L, POEM, DLQI, PGI-S						X							X	X	X			
Tracking of TCS use (Part B subjects only)	X	X	X	X	X	X	X	X	X	X	X	X	X	X	X	X	X	X

Footnotes defined on last page of the table

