6.1 Inclusion Criteria

Subjects are eligible to be included in the study only if all of the following criteria apply:

- 101 Subject has provided informed consent prior to initiation of any study specific activities/procedures
- 102 Age ≥ 18 to ≤ 75 years at screening
- 103 Clinical diagnosis of chronic AD (also known as atopic eczema) for at least 2 years prior to screening and has confirmed AD (Hanifin and Rajka criteria for AD; [Hanifin and Rajka, 1980](#))
- 104 AD that affects $\geq 10\%$ body surface area as assessed by EASI at screening and on day 1
- 105 An IGA score of ≥ 3 at screening and on day 1

- 106 An EASI score of ≥ 16 at screening and on day 1
- 107 Subject discontinued treatment with TCS, topical calcineurin inhibitors (TCI), and prescription moisturizers containing TCS or TCI for at least the 7 days immediately prior to the first dose of investigational product
- 108 Documented recent history (within 12 months before the screening visit) of inadequate response to treatment with topical TCS or subjects for whom topical treatments are otherwise medically inadvisable (ie, because of important side effects or safety risks)
 - Inadequate response is defined as failure to achieve and maintain remission or a low disease activity state (comparable to IGA 0 = clear to IGA 2 = mild) despite treatment with a daily regimen of TCS of medium or higher potency (with or without TCI as appropriate).

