IGA 0/1	response of 0 (clear) or 1 (almost clear) skin on IGA scale
IL	interleukin
IPIM	Investigational Product Instruction Manual
IRB	Institutional Review Boards
INR	international normalized ratio
IUD	intrauterine device
IUS	intrauterine hormonal-releasing system
Interactive Voice Response System (IVRS)	telecommunication technology that is linked to a central computer in real time as an interface to collect and process information
Interactive Web Response System (IWRS)	web based technology that is linked to a central computer in real time as an interface to collect and process information
LDH	lactate dehydrogenase
LKM1	liver kidney microsomal type 1
NASH	nonalcoholic steatohepatitis
NRS	numerical rating scale
PD	pharmacodynamics
PGI-S	Patient Global Impression of Severity
PI	principal investigator

Abbreviation or Term	Definition/Explanation
PK	pharmacokinetics
PRO	patient-reported outcome
POEM	Patient Oriented Eczema Measure
POR	Proof of Receipts
PPD	purified protein derivate
Q2W	every 2 weeks
Q4W	every 4 weeks
QFT-G	QuantiFERON-tuberculosis Gold
Randomization	A subject will undergo randomization upon meeting all eligibility criteria at the day 1 randomization visit
S. aureus	Staphylococcus aureus
SAP	statistical analysis plan
SAT	safety assessment team
SC	subcutaneous
SCORAD	Scoring of Atopic Dermatitis
Source Data	information from an original record or certified copy of the original record containing patient information for use in clinical research. The information may include, but is not limited to, clinical findings, observations, or other activities in a clinical trial necessary for the reconstruction and evaluation of the trial. Source data are contained in source documents (original records or certified copies). (ICH Guideline [E6]). Examples of source data include Subject identification, Randomization identification, and Stratification Value.
Study Day 1	defined as the first day that protocol-specified investigational product(s)/protocol-required therapies is/are administered to the subject
SUSAR	Suspected Unexpected Serious Adverse Reaction
TB	tuberculosis
TBL	total bilirubin
TCI	topical calcineurin inhibitors
TCS	topical corticosteroids
TSLP	thymic stromal lymphopoietin
ULN	upper limit of normal
WHODRUG	World Health Organization Drug Dictionary

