## **5.3 Baseline related definitions**

### Study Baseline

Study baseline is defined as the last non-missing measurement for the endpoint of interest taken **on or before the date of** first dose of investigational product.

**For IGA and EASI, the baseline are the IGA or EASI values collected at “Day 1” visit per protocol schedule of assessment. The values collected at “screening visit” per protocol schedule of assessment could not be used as baseline IGA or EASI.**

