#### **8.3.1 Missing Baseline Value**

Missing baseline evaluations will not be imputed.

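### SAP Appendix A and SAP Section 5.3 give conflicting baseline rules for EASI and IGA; read literally, Appendix A rejects the day-1 value that the protocol collects before randomization

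*SAP*

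**What the plan says.** The SAP states the EASI/IGA baseline twice.

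- **SAP Section 5.3 (Study Baseline):** "For IGA and EASI, the baseline are the IGA or EASI values collected at" the Day 1 visit. Screening values may not be used. Randomization is not mentioned.
- **SAP Appendix A, analysis window for EASI and IGA:** "Last Evaluation after Randomization and prior to or on Study Day 1". The vital-signs table and the table for SCORAD and the questionnaires have a shorter rule: "Last Evaluation prior to or on Study Day 1".

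The protocol fixes the order of events on day 1.

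- **Section 6.1:** criterion 104 sets a minimum "body surface area as assessed by EASI at screening and on day 1". Criteria 105 (IGA) and 106 (EASI) must likewise be met "at screening and on day 1".
- **Table 2-1, footnote o,** on the inclusion criteria re-checked at day 1: "These criteria will be evaluated prior to any other day 1 study activities and are required to be met for dosing with investigational product".
- **Appendix 1:** "A subject will undergo randomization upon meeting all eligibility criteria at the day 1 randomization visit".
- **Table 2-1** places randomization on day 1 and shows one EASI/IGA assessment there. Footnote m makes dosing the last activity of the visit.

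On missing values, SAP Section 8.3.1 says: "Missing baseline evaluations will not be imputed".

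**The concern.** The one EASI/IGA assessment scheduled for day 1 is also the eligibility check, so it comes before randomization by design. An instruction to use only evaluations after randomization points away from that value. Section 5.3 points to it. The SAP does not say which section prevails.

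Baseline EASI is the reference for EASI 75, 50 and 90 and the covariate in the EASI logistic model. Baseline IGA is the covariate in the IGA 0/1 model. The baseline behind both primary analyses should not depend on which section a programmer opens, or on what that programmer takes *after* to mean.

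**Working it through.** The plan gives no figure on this point, so the check is one of wording and timing.

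**Step 1. Order of day 1.** Let E be the day-1 EASI/IGA assessment, R randomization and S the first dose. Footnote o puts E before every other day-1 activity, Appendix 1 puts R after eligibility is met, and footnote m puts S last. By clock time E < R < S. When the schedule is followed, all three share one date, d. SAP Section 5.2 defines Study Day 1 as the first dosing day after randomization, so Study Day 1 is also d.

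**Step 2. Apply the Appendix A row to a correctly timed E.**

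| Reading of *after Randomization* | Condition | Correctly timed baseline |
|---|---|---|
| Clock time | E later than R | Rejected, since E < R |
| Strictly later date | d < date(E) ≤ d | Rejected; the window is empty |
| Same date or later | d ≤ date(E) ≤ d | Kept |

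The third reading still loses a subject whose assessment is dated before randomization. If date(E) = d − 1 and date(R) = d, the condition d ≤ d − 1 fails. Section 5.3 would keep that value if it was recorded as the Day 1 visit.

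For a subject randomized but never dosed, SAP Section 5.2 sets Study Day 1 to the randomization date, so the strictly-later-date window is empty by definition. These subjects stay in the full analysis set (SAP Section 6.1).

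**Step 3. Is there a fallback?** No second day-1 EASI/IGA is scheduled, Section 5.3 bars the screening value, and Section 8.3.1 rules out imputation.

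**Step 4. Consequence for an affected subject, if Appendix A is programmed literally.**

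- *IGA 0/1.* Section 5.5 derives it from the week-16 score and rescue use, so the endpoint survives. The model in Section 9.5.1.1 lacks its baseline IGA covariate.
- *EASI 75.* Section 5.5 gives 1 for at least 75% improvement from baseline without rescue. It sets the endpoint to missing only when there is no week-16 EASI and rescue is absent or unknown. Everything else is 0. With a week-16 EASI but no baseline, the first rule cannot be satisfied and the second does not apply, so the subject is coded 0 whatever the actual response. The covariate is missing too.
- *Other endpoints.* EASI 50 and 90 follow the same derivation (Section 5.6). The models for change from baseline in EASI and IGA (Section 9.5.3.1) also need the value.

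The SAP does not say how a missing covariate is handled. Assuming the usual complete-case logistic fit, the subject drops out of both primary models, while the 0 for EASI 75 would still enter summaries of response percentages.

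**Step 5. Size per subject.** In Part A, 1/60 = 1.7% of an arm. In Part B, 1/40 = 2.5% of the tezepelumab arm and 1/20 = 5% of the placebo arm.

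**The case against.** The best defence is that Section 5.3 is the definitions section and already gives the right value, whereas Appendix A exists to assign assessments to nominal visits. The SAP defines randomization only as a date, and its windows are in whole study days. With randomization and first dose on the same day, the same-date reading is the only one that gives the row any content, and it agrees with Section 5.3. The added words were probably meant to keep screening values out, which Section 5.3 does in plain terms.

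Much of this stands. A careful programmer would probably arrive at the Day 1 value. But the row says *after*, not *on or after*; no rule of precedence settles the conflict; and even the generous reading parts from Section 5.3 when the assessment is dated before randomization.

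Some stronger conclusions are tempting but not supported:

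- *All 240 Part A and 60 Part B baselines will be lost.* That is the bound under a literal reading applied to subjects who follow the protocol order. Section 5.3 and the same-date reading both keep those values.
- *EASI 75 becomes underivable.* Section 5.5 would return 0 for a subject with a week-16 EASI and no baseline.
- *The week-18 switch is affected.* SAP Section 5.2 takes non-responder status from the eCRF, and protocol Section 7.4 compares week 16 with day 1. Appendix A plays no part.
- *A post-randomization baseline would be used instead.* Table 2-1 schedules none on day 1.

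**Conclusion.** The SAP contains two baseline rules for EASI and IGA that disagree for subjects assessed in the protocol's order, and on its literal wording the Appendix A rule is the wrong one. This is a defect of specification, not a demonstrated loss of data.

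The effect ranges from none (Section 5.3 followed, or a same-date reading with every assessment dated on the day of randomization) to rejection of every correctly timed baseline (literal reading). Between these lies the number of subjects whose assessment is dated before randomization, which the documents do not give.

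The conclusion rests on two assumptions: that sites follow footnote o and Appendix 1, and that randomization and first dose fall on the same day as scheduled. Because the row bears on the EASI 75 reference value and on both primary-model covariates, it should be corrected before database lock.

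**What to change.** Replace the baseline row of the EASI/IGA table in SAP Appendix A with: *Day 1 visit evaluation, on or before Study Day 1; screening visit values not used.* Delete the words *after Randomization*.

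The row then matches Section 5.3 and still excludes screening values. Anchoring on Study Day 1 rather than on first dose also covers randomized but never-dosed subjects, for whom a first-dose date does not exist.

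The cost is one table cell, with no new data and no change at the sites.

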7.6 Treatment Compliance

Subjects will receive the SC doses of investigational product at the study centers. The doses will be administered by qualified study personnel for the duration of the study. All efforts should be made to administer investigational product within the defined study windows. In the case of an out of window visit, investigational product can be administered within 1 week of the target visit day (ie, calculated from the day 1 visit). If investigational product cannot be administered within 1 week of the target visit date, the dose is considered missed.

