**13. Appendices**

### Appendix A. Analytical Window for Evaluation

Per protocol, visits are to be performed within 3 days of the protocol-specified study day. To allow for variations in scheduling, the following visit windows will be applied to selected efficacy and safety evaluations (ie, vital signs, laboratory evaluations) to assign a most appropriate nominal visit for analysis. If more than one assigned visit falls within the same defined window, the closest visit to the target day (ie, scheduled visit week  $\times$  7 + 1) will be considered for analysis. If two assessment dates are the same distance from the target day, then the latest visit will be considered for analysis. If more than one evaluation falls on the same date and time for laboratory results, then the value with the smallest accession number will be used.

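### At week 52 a late visit on days 369 to 427 counts for EASI and IGA, but its SCORAD and clinic questionnaires are assigned to no visit

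*SAP*

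**What the plan says.** The introduction to SAP Appendix A restates the visit rule: "Per protocol, visits are to be performed within 3 days of the protocol-specified study day". It then gives the reason for having wider analysis windows: "To allow for variations in scheduling". Where several visits fall in one window, it takes "the closest visit to the target day", which is week × 7 + 1.

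For week 52 the appendix then gives:

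- EASI and IGA: "Study Day 358 to 427", followed by a week-70 row, "Study Day 428 to 494".
- SCORAD, EQ-5D-3L, POEM, DLQI and PGI-S: "Study Day 358 to 368". This is the last row of that table.

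SAP Section 9.5.3.1 uses the week-52 values of SCORAD, PGI-S, POEM and DLQI in exploratory MMRMs for Part A and applies the same methods to Part B. EQ-5D-3L is summarised descriptively. SAP Section 8.3.2 leaves missing continuous endpoints unimputed unless otherwise specified.

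**The concern.** A window that stops at target + 3 on the late side repeats the protocol visit window and adds nothing to it, although the appendix introduces the windows to absorb departures from that schedule. The same visit is then treated in two ways. A subject seen on day 369 has a week-52 EASI and IGA but no week-52 SCORAD, DLQI, POEM, PGI-S or EQ-5D-3L, even though the data were collected.

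Week-52 results for the two groups of instruments would then rest on different sets of subjects, separated only by punctuality. Such visits are foreseeable. Protocol Section 7.6 provides for out-of-window visits: "investigational product can be administered within 1 week of the target visit day". Week 52 carries no dose, so that rule does not govern it, but it shows that visits more than 3 days off target were expected.

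**Working it through.** **Target day.** 52 × 7 + 1 = 365, as the SAP states. The protocol visit window is 365 ± 3, or days 362 to 368.

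**Where the two tables part.**

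| Visit day | Days late | EASI/IGA | SCORAD and questionnaires |
|---|---|---|---|
| 368 | 3 | week 52 | week 52 |
| 369 | 4 | week 52 | none |
| 427 | 62 | week 52 | none |

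The days that count for one table only run from 369 to 427: 427 − 369 + 1 = 59.

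**Late allowance in the SCORAD/questionnaire table** (upper limit minus target):

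| Week | Target | Upper limit | Days late accepted |
|---|---|---|---|
| 4 | 29 | 42 | 13 |
| 8 | 57 | 70 | 13 |
| 12 | 85 | 98 | 13 |
| 16 | 113 | 140 | 27 |
| 24 | 169 | 210 | 41 |
| 36 | 253 | 294 | 41 |
| 48 | 337 | 343 | 6 |
| 50 | 351 | 357 | 6 |
| 52 | 365 | 368 | 3 |

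Every earlier window accepts at least 6 days. From week 16 to week 50 the limits are identical to those for EASI/IGA (99–140, 141–210, 211–294, 295–343, 344–357). Week 52 is the first shared visit after week 12 at which they differ.

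**How the limits arise.** For EASI/IGA, the midpoint between weeks 52 and 70 is (365 + 491)/2 = 428, so week 52 ends on day 427. SCORAD and the questionnaires have no later row, and their table stops at 365 + 3 = 368.

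**Size of the loss.** The documents give no late-visit rate. Let p be the share of week-52 visits after day 368, taken as 5% to 20% by assumption.

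- Observed-case summary: SE ratio = 1/√(1 − p). For p = 0.05, 1/√0.95 = 1.026. For p = 0.20, 1/√0.80 = 1.118. The increase is about 3% to 12%.
- MMRM with AR(1): suppose week 50 is observed, lateness is unrelated to outcome, and the correlation between adjacent visits is r. Then SE ratio ≈ √[1 + (1 − r²)p/(1 − p)]. With r = 0 this reduces to the observed-case formula, which is therefore the upper bound. With r = 0.5 to 0.9 (assumed), the increase is 2.0% down to 0.5% at p = 0.05, and 9.0% down to 2.3% at p = 0.20.

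In Part B (40 and 20 subjects planned), 5% to 20% would be 2 to 8 and 1 to 4 subjects respectively, before dropout.

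**The case against.** The best defence is that the limits follow a consistent pattern. Each window runs to about the midpoint with that instrument's next scheduled assessment, and the last one closes at target + 3. Week 52 accordingly closes on day 385 where week 58 follows (vital signs, hematology, chemistry), on day 427 where week 70 follows (EASI/IGA, pregnancy tests), and on day 368 where nothing follows (SCORAD and questionnaires, coagulation, immunoglobulins). Week 70 closes at 491 + 3 = 494. Nor were the tables meant to match throughout: they differ at weeks 4, 8 and 12, where EASI/IGA has extra visits at weeks 6 and 10. This shows that the limit is not a slip. It does not justify the limit, because no later SCORAD or questionnaire row competes for a value on day 369.

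A second objection also has weight. Day 427 is 427 − 351 = 76 days after the week-50 dose, and DLQI and POEM look back only one week. A very late questionnaire may describe an off-treatment state. That argues about where a common limit should lie, not for different limits at one visit.

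A reader might infer more than the documents support:

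- That compliant visits are lost. They are not: day 369 is already outside the ± 3-day visit window.
- That a 5% to 20% loss is expected. The SAP's reference to COVID-19 says nothing about lateness at week 52.
- That treatment comparisons are biased. Nothing shows that lateness differs by arm.
- That all patient-reported outcomes are affected. Pruritus NRS comes from the daily eDiary and is not in this table.

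**Conclusion.** The inconsistency is real and the day limits are exact. Late week-52 visits on days 369 to 427 contribute EASI and IGA but not SCORAD, EQ-5D-3L, POEM, DLQI or PGI-S, and the SAP gives no reason.

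The point is minor. It touches only exploratory week-52 results in Parts A and B, where any testing is descriptive. The week-16 windows are the same in both tables (days 99 to 140), so the primary endpoints and SCORAD at week 16 are unaffected. The loss cannot be sized from the documents. The 3% to 12% rise in standard error rests on the assumed 5% to 20% late rate. It applies to observed-case summaries and is an upper bound for the MMRM, which still uses a subject's earlier visits.

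**What to change.** End the week-52 window for SCORAD, EQ-5D-3L, POEM, DLQI and PGI-S on day 427, so that all instruments from one visit are analysed together. This changes one table entry, and the closest-to-target rule already settles duplicates. It reduces the mismatched days from 59 to 0.

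The cost is that a few values may come up to 76 days after the week-50 dose. The closest-to-target rule does not exclude such a value when it is the only one. The SAP already accepts this for EASI and IGA.

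If that is a concern, set one shorter limit for both tables, such as day 385, as used for vital signs, hematology and chemistry. That allows 385 − 365 = 20 days late and lies 385 − 351 = 34 days after the week-50 dose. It changes two entries, and EASI/IGA values on days 386 to 427 would then need a stated rule, because the week-70 row starts on day 428.

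Either change should be recorded with its reason before the week-52 data are examined by arm.
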